### **BOX 1. ACOG's 5A's**

1. **ASK** the patient about smoking status at the 1st prenatal visit and follow-up with her at subsequent visits.
  - A. I have never smoked or I have smoked fewer than 100 cigarettes in my lifetime
  - B. I stopped smoking before I found out I was pregnant and I am not smoking now
  - C. I stopped smoking after I found out I was pregnant, but I am not smoking now
  - D. I smoke now, but I cut down on the number of cigarettes I smoke since I found out I was pregnant
  - E. I smoke regularly now, about the same as before I found out I was pregnant
2. **ADVISE** the patient who smokes to stop by providing advice to quit with information about the risks of continued smoking to the woman, fetus, and newborn.
3. **ASSESS** the patient's willingness to attempt to quit smoking at the time. Quitting advice, assessment, and motivational assistance should be offered at subsequent visits.
4. **ASSIST** the patient willing to make an attempt using counseling and pharmacotherapy to help her quit.
5. **ARRANGE** the follow-up contact, in person or by telephone, preferably within the first week after the quit date.

Usual Care (TTAU): Eligible women randomized to the control group will be informed of the risks of tobacco use and benefits of quitting using the ACOG 5A's approach by their healthcare provider. This standard takes approximately 5-15 minutes, and is offered at each prenatal and postpartum appointment. The research nurse or key personnel will invite participants to complete the tobacco use questionnaires (TUQ), urine cotinine validation, and Expired Air Carbon Monoxide (EACO) analysis to assess ongoing tobacco use at the designated time points; participants will receive a monetary gift card as compensation for their time, at the denominations listed below in Table 1.

The Intervention (ToPIC): Eligible women randomized to the intervention will receive TTAU plus ToPIC administered by the CTTS. At least once monthly, at routinely scheduled prenatal visits or through telephone, the CTTS will provide cessation counseling (see components of a typical counseling session in Box 2). The CTTS will invite participants to complete TUQs, urine cotinine validation and EACO analysis to assess ongoing tobacco use at the designated time points; participants will receive a monetary gift card as compensation for their time. See summary of study procedures in Table 1.

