## **Study Protocol:**

**Study Design:** The effectiveness-implementation hybrid design of this proposal enables the simultaneous evaluation of both effectiveness outcome measures as well as of the process of implementation. We propose a type 2 hybrid trial to test both the effectiveness of the clinical intervention (the 5A's delivered via a CTTS) while simultaneously gathering multi-level contextual data regarding potential barriers and facilitators to clinical implementation. Effectiveness questions will be explored using a two-armed cluster randomized controlled design. Implementation questions include: (1) what are the facilitators/barriers to delivering tobacco treatment to pregnant women using existing healthcare provider in the clinic settings; (2) how likely is intervention delivered as prescribed (fidelity); (3) what implementation strategies might maximize the facilitators and overcome barriers to implementation; and (4) what potential modifications could be made to maximize implementation? This pilot project will gather quantitative and qualitative data for a mixed-method, multi- stakeholder process evaluation of intervention training and delivery among 12 clinic staff and providers involved in the project. Furthermore, our use of Medicaid claims data will enhance understanding of the strengths and limitations of these data for future evaluations.

**Aim 1 - Effectiveness evaluation:** As part of routine standard of care, all pregnant Medicaid patients who receive first trimester screening through the intervention or Tobacco Treatment as Usual (TTAU) clinic will also be asked about their tobacco use consistent with the ACOG recommended questionnaire (the standard of care for TTAU is the ACOG recommended questionnaire in Box 1. ACOG 5A's). All women who report tobacco use would be considered eligible to participate to receive ToPIC or TTAU. Participants in the intervention and TTAU clinics will be informed their urine will be tested for cotinine to confirm tobacco use at each data collection point and be informed of their results in compliance with ACOG clinical standards. Inclusion criteria are: 1. Pregnant and age 18-44; 2. Tobacco user (self-reported) 3. Can read and write in English; and 4. Medicaid subscriber.

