## BOX 2. Typical Counseling Session with a CTTS for Pregnant Women

- Assessment of tobacco use and tobacco use history using an evidence-based tool
- Motivational and practical counseling based on assessment of readiness, including providing education on the maternal and fetal health impacts of smoking
- Provide strong advice to quit as soon as possible
- Exploration of the pros and cons of tobacco use/quitting (decisional balance) and triggers/cues to smoke, including partner smoking and potential engagement in treatment
- Collaboratively developing a tailored treatment plan, which may include but is not limited to incentives, and trigger management strategies, such as stress management or partner support
- Setting a quit date with close follow up
- Discussion relapse prevention strategies during the perinatal and postpartum periods

Our target sample size is 60 participants in each the intervention and control group, for a total of 120 pregnant participants for this pilot project. Additionally, 12 clinic staff and providers will provide quantitative and qualitative data for a mixed-method, multi-stakeholder process evaluation of intervention training and delivery. Due to our limitation of only two participating clinics, we acknowledge that it will not be possible to fully distinguish the effects of the intervention from differences between the two clinic populations. A future larger study of this intervention will include a true group randomized trial, with multiple clinics per treatment, so that the effect of nesting of patients within clinics within treatment will be estimable. In light of this limitation, we will use sample demographic characteristics as covariates in the repeated measures mixed modeling; we acknowledge that the group effects are still likely to be somewhat inflated in this analysis, given the expected artificially small errors due to correlations among patients who visit the same clinic and who may see the same provider. Although we will have limited power, the results from this pilot proof-of-concept study will provide preliminary data to support a highly competitive NIH Health Care Systems Research Pragmatic Trial application.

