in this way, the emphasis on the analysis will be the detection of average differences between the groups, so that we may use this to estimate effect sizes for a larger study in the future. With 60 participants per group and an alpha level of .05, the power of the repeated measures mixed model F test will have at least 90% power to detect a medium effect in the context of group differences, time differences, or a group by time interaction. A medium effect is such that the ratio of the standard deviation of the group means to the standard deviation of the observations within the populations is at least 0.25. While an effect size driven algorithm for estimating the power associated with GEE models has not been developed, logistic regression is considered as a similar technique. With 120 participants and an alpha level of .05, the power of logistic regression to detect an odds ratio as small as 2.3 will be at least 91%. One way to attain an odds ratio of this magnitude would be if the percent of participants in each group with a particular outcome were 50% versus 30%. The power associated with the corresponding GEE model (and extension of logistic regression to the longitudinal application) is expected to be at least as large, given the additional time points included. Power estimates were obtained using nQuery Advisor, v. 6.02 (Elashoff, J. 1995-2005. nQuery Advisor, Statistical Solutions. Saugus, MA).

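### Arm coincides with clinic, one clinic per arm, but the plan describes women as randomized and tests and powers the group effect at alpha .05 as if 120 women were independent; the clinic caveat it admits never reaches the analysis.

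*Combined protocol and SAP*

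**What the plan says.** The plan describes allocation in three ways.

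- **Study Design paragraph:** "Effectiveness questions will be explored using a two-armed cluster randomized controlled design".
- **Aim 1:** women come through "first trimester screening through the intervention or Tobacco Treatment as Usual (TTAU) clinic", so each arm is identified with a clinic. The paragraph after Box 2 confirms the count: "Due to our limitation of only two participating clinics".
- **Usual Care and Intervention paragraphs after Box 1:** "Eligible women randomized to the control group will be informed of the risks of tobacco use" and "Eligible women randomized to the intervention will receive TTAU plus ToPIC administered by the CTTS".

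The paragraph after Box 2 sets the size ("Our target sample size is 60 participants in each the intervention and control group") and is candid about the limits. It concedes that the intervention cannot be fully distinguished from differences between the clinic populations. It defers a proper group randomized trial with several clinics per arm, and it calls power limited. It expects group effects to look somewhat inflated, "given the expected artificially small errors due to correlations among patients who visit the same clinic and who may see the same provider". The response offered is demographic covariates in the mixed model.

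The SAP tests group and group-by-time effects with mixed models for continuous outcomes and GEE for categorical ones. Covariates there are optional, depending on bivariate association with outcome. Power is given at alpha .05 as at least 90% (mixed model, medium effect) and at least 91% (logistic regression, odds ratio 2.3, illustrated by 50% versus 30%). The SAP names the planning of a later, bigger trial as the purpose: "the emphasis on the analysis will be the detection of average differences between the groups, so that we may use this to estimate effect sizes".

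**The concern.** With one clinic per arm, any difference between the clinics in patients, providers or routine practice is part of the arm contrast, and the data contain nothing from which clinic-to-clinic variation could be estimated. A model that treats women as the independent units uses a standard error that omits this component. Demographic covariates may reduce confounding by the factors measured; they do not supply a clinic error term or remove unmeasured clinic differences.

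Even that partial remedy is not secured for the primary outcome. Third-trimester cessation is dichotomous, so it goes to GEE. The firm promise of covariates is made for the mixed model, while the SAP's own rule is conditional.

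Two things are at stake. A nominally significant group effect could be read as evidence that ToPIC works. And the effect size passed to the larger trial would carry the clinic difference with it. A reader who sees only the arm descriptions would also conclude that individuals were randomized.

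**Working it through.** **Inputs from the documents:** 2 clinics, 2 arms, 60 women per arm, alpha .05, 50% versus 30% as the example. **Assumed:** two-sided testing (sidedness is not stated), clinic ICC of 0.01 to 0.05 (none is given), and cessation of about 40%, the midpoint of the example.

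**1. The plan's power figures, taking women as independent.**
- *Binary.* Null standard error √(2 × 0.24/60) = 0.0894; alternative standard error √((0.25 + 0.21)/60) = 0.0876. Power = Φ[(0.20 − 1.96 × 0.0894)/0.0876] = Φ(0.28), about 61%. One-sided it is about 73%. The stated 91% is not reproduced; it would need 129 women per arm. A figure near it (90.8%) comes from a logistic formula for a continuous covariate, with odds ratio 2.3 per standard deviation and a 30% event rate. That is not a two-arm comparison.
- *Continuous.* f = 0.25 with 120 women gives 77.5% at one time point. With three visits the between-group test reaches 91.4% if the within-woman correlation is 0.5, and 88.7% if it is 0.6. No correlation is stated, so the 90% is attainable but conditional.

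Neither calculation contains a clinic component.

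**2. Degrees of freedom.** 2 clinics − 2 arms = 0 for clinic error within arm. A permutation test over two clinics has a smallest two-sided p-value of 1.0.

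**3. Effect of ignoring clinic.** Design effect DE = 1 + (60 − 1) × ICC. True type I error of the nominal test = 2 × [1 − Φ(1.96/√DE)]. Half-width of a 95% interval = 1.96 × √(2 × 0.24/60 × DE). Standard deviation of the difference between two clinics with no treatment effect = √(2 × ICC × 0.24).

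| Assumed ICC | DE | True type I error | Half-width (points) | SD of clinic difference (points) |
|---|---|---|---|---|
| 0 | 1.00 | 5% | 17.5 | 0 |
| 0.01 | 1.59 | 12.0% | 22.1 | 6.9 |
| 0.02 | 2.18 | 18.4% | 25.9 | 9.8 |
| 0.05 | 3.95 | 32.4% | 34.8 | 15.5 |

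A beta-binomial simulation (one clinic per arm, 30% rate, 200,000 runs) gave type I errors of 12.4%, 19.1% and 33.8% at ICC 0.01, 0.02 and 0.05, in line with the formula. For scale, the plan's example difference is 50 − 30 = 20 points.

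**4. Scope.** DE applies to the group difference at one time point. It does not carry over to group-by-time: a clinic difference that is constant over time cancels from that contrast on the model scale, and only clinic-by-time variation distorts it.

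**The case against.** The strongest defence is disclosure. The paragraph after Box 2 states both consequences, confounding with clinic and understated errors. It calls the study a pilot proof of concept, concedes limited power and defers the proper design. That stands, and it lowers the severity. It does not settle the matter, because the SAP still relies on the tests and states power without the caveat.

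Several stronger readings that a reader might infer are not supported:

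- *That the trial is not cluster randomized.* The documents do not say how the two clinics were assigned. If by chance, the label is formally correct, though uninformative with one clinic per arm. The wording about women being randomized may be loose phrasing for women in a randomized clinic.
- *That the plan's confidence intervals are wrong.* It specifies none. One can say only that an interval from these models would be too narrow if the ICC is above 0.
- *That the word inflated asserts a direction of bias.* The sentence ties it to small errors, which is a statement about overstated significance. What it leaves unsaid is that the clinic difference can move the estimate either way.
- *That the p-values are wrong by a known amount.* No ICC is given and none can be estimated here, so the sizes are conditional.
- *That the group-by-time test fails for the same reason and by the same factor.* It does not, as step 4 of the working shows.

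**Conclusion.** The point holds in a limited form. Arm and clinic coincide, the arm descriptions conflict with the rest of the protocol, and the SAP's group tests and power statements ignore a limitation that the protocol itself admits. For any clinic ICC above 0 the nominal .05 group test is anti-conservative. Over an assumed 0.01 to 0.05 the true type I error is about 12% to 32%, and the half-width for a cessation difference is 22 to 35 points rather than 17.5, assuming 60 women per clinic and about 40% cessation. Even with independent women, the 91% is about 61% for the plan's own example.

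A reader might go further and conclude that the sponsor concealed the problem or that the study is worthless. The documents support neither: the limitation is disclosed, and the stated emphasis is on estimating effect sizes. This is a should-fix.

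**What to change.** 1. **Allocation wording.** In the Usual Care and Intervention paragraphs, say that women receive the arm of their clinic. In the Study Design paragraph, state that there is one clinic per arm and how the clinics were assigned; keep the cluster randomized label only if assignment was random.
2. **Analysis.** In the SAP, report the average arm difference as an estimate, with an interval recomputed over assumed ICCs (variance × (1 + 59 × ICC)) and labelled a sensitivity range. Do not treat p < .05 for the group effect as evidence of effectiveness. Interpret group-by-time as exploratory, noting that a stable clinic difference cancels on the model scale but clinic-by-time differences do not.
3. **Power.** State that the figures ignore clinic and do not apply to the between-clinic comparison. Do not keep the 91% even for independent women.
4. **Next trial.** Carry the ICC-widened range into its planning.
5. **Limitations paragraph.** Clarify that standard errors will be too small and that the clinic difference may bias the estimate in either direction.

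The cost is protocol and SAP wording, a few extra lines of analysis and a less favourable claim. No additional participants, clinics or staff are needed.

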**Table 1. Summary of Study Procedures**

Time points	ToPIC participants	TTAU participants	Outcome	Compensation
Pregnant Patient Participants:				
Baseline <20 weeks gestation	
 
• Urine cotinine
 
• EACO
 
• ACOG tobacco use screen
 
	
 
• Urine cotinine
 
• EACO
 
• ACOG tobacco use
 
	Eligibility screen for tobacco	\$10
Monthly through end of pregnancy at regularly scheduled prenatal visits	
 
• CTTS tobacco treatment education support, including
 
• Individualized treatment plan (baseline)
 
• 5As
 
• Motivational Interviewing
 
• Navigation to resources
 
	
 
• 5As, as per usual
 
		
28-34 weeks gestation	
 
• Urine cotinine
 
• EACO
 
• TUQ
 
	
 
• Urine cotinine
 
• EACO
 
• TUQ
 
	Tobacco cessation or reduction	\$10
Postpartum 2-8 weeks after delivery	
 
• Urine cotinine
 
• EACO
 
• TUQ
 
	
 
• Urine cotinine
 
• EACO
 
• TUQ
 
	Tobacco cessation or reduction	\$20
Postpartum 12-18 weeks after delivery	
 
• Urine cotinine
 
• EACO
 
• TUQ
 
	
 
• Urine cotinine
 
• EACO
 
• TUQ
 
	Tobacco cessation or reduction	\$20

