### Statistical Analysis Plan

Analysis and estimated power: **Primary outcome:** The primary outcome is smoking cessation in the third trimester, defined as urine cotinine level of <100 ng/mL. **Secondary outcomes** include: self-reported number of cigarettes smoked/day, smoking cessation after delivery, infant birth weight, gestational age at delivery, health care utilization outside of scheduled normal prenatal and infant well-child visits. Two-factor mixed models with group by time interactions will be employed to analyze longitudinal continuous data collected over the course of the trial. Significant main and interaction effects will be explored further using Tukey post-hoc tests. Generalized estimating equation (GEE) modeling will be used to test for significant differences between groups and across time for categorical and dichotomous outcomes; these models will also consider possible group by time interactions. Post-hoc analysis of significant main or interaction effects in the GEE models will be accomplished using contrasts. Demographic and personal factors (e.g., maternal age, gestational age at enrollment) may be included as covariates if linked to outcomes in bivariate analysis. We **hypothesize** that compared with the TTAU group, the ToPIC group will have higher tobacco cessation rates, fewer infants born preterm, and fewer ill child health care visits. While we will assess group differences over time

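### The treating counsellor invites women to the smoking measures in ToPIC but research staff do so in TTAU, so self-reported cigarettes/day could be misreported differently by arm

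*Combined protocol and SAP*

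**What the plan says.** The two paragraphs after Box 1 in the Study Protocol assign the outcome contact to different roles.

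- **ToPIC:** "The CTTS will invite participants to complete TUQs, urine cotinine validation and EACO analysis to assess ongoing tobacco use at the designated time points". Earlier in the same paragraph, "the CTTS will provide cessation counseling" at least monthly. Box 2 lists among the contents of a session: "Provide strong advice to quit as soon as possible". It also lists setting a quit date.
- **TTAU:** "The research nurse or key personnel will invite participants to complete the tobacco use questionnaires (TUQ), urine cotinine validation" and the expired-air test. The 5A's advice in this arm comes from the healthcare provider.

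The Statistical Analysis Plan defines the primary outcome as "smoking cessation in the third trimester, defined as urine cotinine level of <100 ng/mL". The first two secondary outcomes listed are "self-reported number of cigarettes smoked/day, smoking cessation after delivery". Table 1 schedules the TUQ, urine cotinine and expired-air test at "28-34 weeks gestation" and at two postpartum windows, with the same measures and payments in both arms. Under Aim 1, women in both clinics are told that their urine will be tested at each data collection point.

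The documents do not say how the TUQ is completed or who reads it. The limitations paragraph after Box 2 admits that clinic and intervention cannot be fully separated, but does not mention this difference in who approaches the women.

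**The concern.** A woman who has been counselled for months by one person, and has perhaps agreed a quit date with that person, may give a lower cigarette count when the same person hands her the questionnaire. In TTAU the plan names a different role from the one that gives the advice. If reporting differs for this reason, the group contrast in cigarettes/day mixes a treatment effect with a reporting effect.

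The planned analysis cannot separate the two. Every ToPIC woman is approached by the CTTS and every TTAU woman by research staff, so the source of the invitation is the same variable as arm. Adjusting for maternal age, gestational age at enrolment or other demographics leaves it untouched. Repeated measurement does not help either, because the same arrangement applies at each follow-up.

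This matters for the pilot's own purpose. The Statistical Analysis Plan puts the emphasis on average group differences, to supply effect sizes for a larger study. Confounding by clinic follows from having only two clinics. This difference is procedural and can be changed.

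**Working it through.** **1. Which outcomes are exposed**

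| Outcome | How measured | Exposure |
|---|---|---|
| Third-trimester cessation (primary) | Urine cotinine, fixed cut-off | Not through the reading; only through timing or completeness of samples |
| Cigarettes/day (secondary) | Self-report | Direct |
| Cessation after delivery (secondary) | Cotinine is taken postpartum, but the cotinine definition is stated only for the third trimester | Unclear until defined |

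The TUQ is the only smoking questionnaire in Table 1 at follow-up, so I take it to be the source of cigarettes/day. The documents do not say so outright.

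**2. Self-report: an illustration**

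The documents give no figure for reporting bias, so there is none to reproduce.

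- From the documents: 60 per arm (target sample size), alpha .05.
- Assumed: two-sided test, SD of cigarettes/day 6 to 8, no true effect, no attrition, one time point, and ToPIC women under-reporting by u cigarettes/day more than TTAU women.

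Spurious standardised difference: d = u/SD. Its standard error in SD units is sqrt(2/60) = 0.183. The false-positive rate is Φ(d/0.183 − 1.96) + Φ(−d/0.183 − 1.96).

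| u | SD | d | d/0.183 | False-positive rate |
|---|---|---|---|---|
| 1 | 6 | 0.17 | 0.91 | 15% |
| 1 | 8 | 0.13 | 0.68 | 11% |
| 2 | 6 | 0.33 | 1.83 | 45% |
| 2 | 8 | 0.25 | 1.37 | 28% |

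For scale, the Statistical Analysis Plan calls an effect medium when the SD of the group means is 0.25 of the within-population SD. With two equal groups the SD of the means is half their difference, so medium is d = 2 × 0.25 = 0.5. A 1/day shift is then 0.125/0.5 = 25% to 0.167/0.5 = 33% of a medium effect.

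**3. Cotinine timing: a worst case**

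Assume two possible sampling visits in the six-week window, the favourable one always used in ToPIC and never by choice in TTAU, and a true rate of 30% in both arms (the lower rate in the plan's own example). With within-woman correlation ρ, the observed ToPIC rate is 1 − (0.7² + ρ × 0.3 × 0.7). The false-positive rate is for a two-sided pooled z-test with 60 per arm.

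| ρ | Observed ToPIC rate | Odds ratio | False-positive rate |
|---|---|---|---|
| .9 | 32.1% | 1.10 | 5.7% |
| .8 | 34.2% | 1.21 | 7.8% |
| .5 | 40.5% | 1.59 | 22% |
| .2 | 46.8% | 2.05 | 47% |

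If cotinine status is stable between visits, even systematic choice of the sampling visit does little. The large figures need both that choice and unstable status, and the documents support neither.

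**The case against.** The strongest reply is that the text claims less than a reader might infer from it.

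- **Invitation is not collection.** Both paragraphs use the same verb, to invite women to complete the measures. A reader might infer that the counsellor asks the questions and records the answers. The documents do not say so. Women must be able to read and write English, so self-completion is quite possible. This stands: the defect is that the mode is unstated and the inviter differs by arm.
- **Research staff may not be neutral.** A reader might infer that TTAU women face someone with no part in treatment. The other duties of the research nurse and key personnel are not described. This also stands.
- **Pressure to please exists in both arms.** TTAU women receive quit advice at every prenatal and postpartum appointment, and both arms know that their urine is tested. This should discourage misreporting. It is a partial safeguard, because a cotinine test known in advance does not verify a cigarette count.
- **The direction is not fixed.** Rapport with a counsellor could increase candour. Bias in favour of ToPIC is the likelier direction, but the documents cannot establish it.
- **A false-positive rate is an awkward yardstick.** The plan already concedes artificially small errors and clinic confounding, and its emphasis is on estimation. I agree that the spurious standardised difference is the more useful number.

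**Conclusion.** The concern holds for self-reported cigarettes/day. The person inviting women to the measure differs by arm, the TUQ mode is unstated, the limitations paragraph does not acknowledge the difference, and no planned covariate can remove its effect. The outcome could be under-reported differently by arm. The documents do not show that it will be, or by how much.

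On the assumed SD of 6-8, 60 per arm and no true effect, a differential of 1/day gives a spurious standardised difference of 0.13-0.17 and about 11-15% false positives against a nominal 5%. Both the SD and the size of under-reporting are assumptions, so these figures show sensitivity and are not estimates.

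A reader might also infer that the primary outcome is compromised because the counsellor could choose when to ask for the sample or how hard to pursue it. The documents do not support that. Samples are tied to designated time points, and the outcome is a laboratory value with a fixed cut-off. The timing and completeness routes remain possible but speculative, so the primary outcome is largely protected.

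**What to change.** State one TUQ procedure for both clinics: the woman completes the form herself before the counselling or clinic session, seals it, and neither the CTTS nor the treating provider sees it. Where research staff are already available at the ToPIC clinic, have them, rather than the CTTS, invite women to the outcome measures.

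The cost is protocol wording and minor form handling. The CTTS could not use the TUQ answers in counselling, but Box 2 already gives the CTTS a separate assessment of tobacco use within the session.

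Two further steps should not be made conditions. Moving all ToPIC follow-up to research staff could mean 60 × 3 = 180 collections by people whom the plan places only in TTAU. Fixing the cotinine sample at the first visit from 28 weeks would limit choice of timing, but it would move the primary endpoint to the early edge of its window, which is a trade-off for the sponsor to weigh.
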